2.3. Hypotheses

All primary and secondary hypotheses must be met in order to satisfy the objective of this study.

Primary Hypotheses

1. After approximately 2 weeks of wear, the mean overall quality of vision score of the Test lens will be statistically better than 40 points on CLUE scale.
2. After approximately 2 weeks of wear, the Test lens will be non-inferior to the Control lens with respect to the overall quality of vision score. A non-inferiority margin of 5 points will be used.

Secondary Hypotheses

1. After approximately 2 weeks of wear, the mean distance visual acuity score of the Test lens will be statistically lower than 0.00 on logMAR scale.
2. After approximately 2 weeks of wear, the mean intermediate visual acuity score of the Test lens will be statistically lower than 0.17 on logMAR scale.
3. After approximately 2 weeks of wear, the mean near visual acuity score of the Test lens will be statistically lower than 0.17 on logMAR scale.

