3.3	Compliance	
Record the subject's compliance with wearing the study lenses.
 
NOTE: Subjects must have worn lenses for at least 6 hours per day. To be counted as a day of wear at this visit the Subject must have worn the study lenses for 6 hours prior to the visit.
	
3.4	PRO (CLUE and MRD) and CLDEQ-8 Questionnaires	The subject will evaluate the vision characteristics, comfort characteristics, handling characteristics, and visual symptoms of the study lenses using the PRO (CLUE and MRD) questionnaires.	
3.5	Ocular Symptoms	Subjects will respond to a verbal open-ended symptoms questionnaire	
3.6	Subjective Acceptance	Record whether the subject's distance and near vision with the lenses is acceptable.	

Clinical Study Protocol
Johnson & Johnson Vision Care, Inc.

3.7	Distance and Near Entrance Visual Acuity	
Measure the distance and near visual acuity OD, OS and OU. Record the results.
 
For near measures use the ETDRS 2000 Series Chart 1 or 2. The acuity will be recorded to the nearest letter OD, OS and OU.
	
3.8	Visual Performance Distance (4M) Intermediate (64 cm) Near (40 cm)	
Visual performance will be recorded OD, OS, and OU for the following:
 
Distance, Bright Illuminance High and Low Contrast ETDRS Charts 4M- HC#1, HC#2, HC#3 and LC#1, LC#2, LC#3
 
Near, Bright Illuminance Reduced Guillon-Poling Charts Intermediate (64 cm) High Contrast and Low Contrast Near (40 cm) High Contrast and Low Contrast
 
Distance, Dim Illuminance (with Distance goggles) High Contrast ETDRS Charts 4M-HC#4, HC#5, HC#6
 
Near, Dim Illuminance (with Near goggles) Reduced Guillon-Poling charts High Contrast Intermediate (64 cm) and Near (40 cm).
 
NOTE:
 
 • The room illuminance must be between 7.3 and 7.9 EV (394-597 lux). • Distance, HC-1 Chart luminance Acceptable Range 10.5-10.7 EV (181-208 cd/m²). • Guillon-Poling, Near Chart Luminance Acceptable Range 10.8-11.1 EV (223-274 cd/m²). • Do not use the Mesopic filter for Dim luminance (Dim luminance will be simulated by using the goggles) 	
3.9	Binocular Distance Over-refraction and Distance Visual Acuity	
Perform a binocular over-refraction and record the OD and OS results and distance visual acuity.
	

Clinical Study Protocol
Johnson & Johnson Vision Care, Inc.

		Note: No lens changes are allowed based on the over-refraction.	

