14.5. Primary Analysis

All primary analysis will be conducted on the Per-protocol population.

CLUE Vision

CLUE vision scores at the 2-week follow-up will be analyzed using a linear mixed model adjusting for baseline values as a covariate. Sequence of lens wear, study period, lens type will be included as fixed effects. Other factors such as, race, gender or ADD power may be included in the model as covariates when appropriate. Site will be included as a random effect (G-side). The covariance between residual errors from the same subject across study periods will be modeled using either homogenous compound symmetry (CS) or unstructured (UN). The

Clinical Study Protocol

Johnson & Johnson Vision Care, Inc.

structure that returns the lowest finite-sample corrected Akaike's Information criterion⁷ will be selected as the structure that best fits the model. The Kenward and Roger method, (Kenward and Roger, 1997)⁸ will be used for the denominator degrees of freedom.

Comparisons between the Test and Control lens at the 2-week follow-up evaluation will be carried out using two-sided 95% confidence intervals constructed for the least-square mean difference (Test minus Control).

Primary hypothesis 1:

The null and alternative hypothesis for CLUE vision to test for superiority of the Test lens relative to the pre-defined threshold of 40 is as follows:

$$H_0: \mu_{Test} \leq 40$$
$$H_A: \mu_{Test} > 40$$

Superiority will be declared if the lower limit of the 95% confidence interval of the adjusted mean for the Test lens is greater than 40. i.e. $P(\mu_{Test} > 40) \geq 0.975$.

Primary Hypothesis 2:

The null and alternative hypothesis for CLUE vision to test for non-inferiority of the Test lens relative the Control lens is as follows:

$$H_0: \mu_{Test} - \mu_{Control} \leq -5$$
$$H_A: \mu_{Test} - \mu_{Control} > -5$$

Non-inferiority will be declared if the lower limit of the 95% confidence interval for the least-square mean difference is greater than -5. i.e. $P(\mu_{Test} - \mu_{Control} > -5) \geq 0.975$.

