14.6. Secondary Analysis

Visual Performance (logMAR)

Binocular, high luminance, high contrast visual performance (logMAR) will be analyzed using a linear mixed model. Sequence of lens wear, study period, lens type, distance (4m, 64cm and 40cm) and the lens by distance interaction as fixed effects. Other characteristics including, age, gender and race and ADD power may be included when appropriate. Site will be included as a random effect (G-side). The covariance between residual errors from the same subject and distance across study periods will be modeled using either homogenous compound symmetry (CS) or unstructured (UN) covariance structure. The structure that returns the lowest finite-sample corrected Akaike's Information criterion⁷ will be selected as the structure that best fits the model. The Kenward and Roger method⁸ will be used for the denominator degrees of freedom.

Clinical Study Protocol

Johnson & Johnson Vision Care, Inc.

Comparisons between the Test and Control lenses will be carried out at each distance (4m, 64cm and 40cm) using 2-sided 95% confidence intervals constructed of least square means (LSM) differences (Test minus Control) at the 2-week follow-up evaluation.

Secondary hypothesis 1:

The null and alternative hypothesis for binocular distance HLHC visual performance to test for superiority of the Test lens relative to the pre-defined threshold of 0 logMAR is as follows:

$$H_0: \mu_{Test} \geq 0 \text{ logMAR}$$
$$H_A: \mu_{Test} < 0 \text{ logMAR}$$

Superiority will be declared if the upper limit of the 95% confidence interval of the adjusted mean for the Test lens is below 0 logMAR. i.e. $P(\mu_{Test} < 0) \geq 0.975$.

Secondary hypothesis 2:

The null and alternative hypothesis for binocular near HLHC visual performance to test for superiority of the Test lens relative to the pre-defined threshold of 0.17 logMAR is as follows:

$$H_0: \mu_{Test} \geq 0.17 \text{ logMAR}$$
$$H_A: \mu_{Test} < 0.17 \text{ logMAR}$$

Superiority will be declared if the upper limit of the 95% confidence interval of the adjusted mean for the Test lens is below 0.17 logMAR. i.e. $P(\mu_{Test} < 0.17) \geq 0.975$.

Secondary hypothesis 3:

The null and alternative hypothesis for binocular distance HLHC visual performance to test for superiority of the Test lens relative to the pre-defined threshold of 0.17 logMAR is as follows:

$$H_0: \mu_{Test} \geq 0.17 \text{ logMAR}$$
$$H_A: \mu_{Test} < 0.17 \text{ logMAR}$$

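### Section 14.6 links a subject's three acuity distances only through site; if they are positively correlated and there are about five or more sites, the Test-mean intervals are on average about 2–8% wider than needed

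*Combined protocol and SAP*

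**What the plan says.** Section 14.6 fits a single linear mixed model to binocular, high-luminance, high-contrast logMAR acuity. The fixed part reads "Sequence of lens wear, study period, lens type, distance (4m, 64cm and 40cm) and the lens by distance interaction as fixed effects". For the errors, the plan models "The covariance between residual errors from the same subject and distance across study periods" as compound symmetric or unstructured and picks between the two by corrected AIC. Site is the only random effect named.

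Section 14.5, for CLUE vision, defines the error block without distance: "The covariance between residual errors from the same subject across study periods".

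Section 7.2 (steps 3.8 and 6.8) has the same subject read at all three distances at Visits 3 and 6: "Visual performance will be recorded OD, OS, and OU for the following", followed by the list of distances and lighting conditions.

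For the first secondary hypothesis the rule is "Superiority will be declared if the upper limit of the 95% confidence interval of the adjusted mean for the Test lens is below 0 logMAR". The intermediate and near hypotheses use the same form with a threshold of 0.17. Section 2.3 adds: "All primary and secondary hypotheses must be met in order to satisfy the objective of this study".

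**The concern.** Each subject supplies 3 distances × 2 periods = 6 binocular readings. Adding distance to the block definition splits these into three blocks of two, and nothing else in section 14.6 restores the subject level. Under the written model, one person's readings at 4 m and 40 cm are no more alike than readings from two different people at the same site.

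If people who read well at one distance tend to read well at the others, site averages will vary more than the residual part of the model allows. The only place for the excess is the site variance, and that component enters the standard error and degrees of freedom of every Test-lens mean. This happens even when the SD is the same at all three distances. The affected intervals decide three of the five tests that must all succeed.

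**Working it through.** **Inputs from the documents.** 70 subjects targeted to complete (section 4.1); multi-site, number not given (section 4.1); thresholds 0.00 at distance and 0.17 at intermediate and near (section 2.3); earlier Test-lens means of -0.057 at distance and 0.091 at near (section 1.5); Kenward-Roger degrees of freedom (section 14.6). The plan gives no acuity SD, between-distance correlation or acuity power, so there is no stated figure to reproduce.

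**Assumptions.** Per-reading variance σ² = 1; correlation 0.75 between the two periods at one distance; common between-distance correlation r of 0 to 0.7; true site variance 0 or 0.05; SD of 0.10 to 0.15 logMAR for power.

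**Closed form (balanced sites, before truncation at zero).** Let c = rσ² be the covariance shared across distances.

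- Averaged over a subject's readings, c contributes c to the true variance. The written model sees it only inside the three separate blocks, so it allows c/3. The excess is c − c/3 = (2/3)c.
- Expected site-variance estimate = true value + (2/3)c/n_site, with n_site subjects per site.
- Modelled variance of a Test mean is too large by (2/3)c/N. With no true site variance the factor is 1 + (2/3)r.

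| r | variance factor | SE factor |
|---|---|---|
| 0.3 | 1.20 | 1.10 |
| 0.5 | 1.33 | 1.15 |
| 0.7 | 1.47 | 1.21 |

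With 7 sites (n_site = 70/7 = 10) and r = 0.5, the expected excess site variance is (2/3)(0.5)/10 = 0.033.

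**Simulation of the practical comparison.** The written model was compared with the same model plus a subject effect. Site variance was truncated at zero, and Satterthwaite degrees of freedom stood in for Kenward-Roger.

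- 7 sites, r = 0.5, no true site variance: mean site variance 0.036 as written against 0.015 corrected; site variance above zero in 84% against 43% of runs; coverage 97.4% against 96.4%; mean half-width ratio 1.07.
- 5 to 10 sites, r from 0.3 to 0.7: half-width ratio 1.04 to 1.11 with no true site variance, and 1.02 to 1.10 with site variance 0.05. At 10 sites and r = 0.5 the ratios are 1.082 and 1.076, which sets the upper end of about 8% for r up to 0.5.
- Repeating with within-distance correlation 0.7 and no true site variance: 4–5% wider at r = 0.3 and 6–8% at r = 0.5.
- Seven unequal sites fitted by REML (95 to 99 runs): SE ratio 1.05 at r = 0.3 and 1.09 at r = 0.5.
- r = 0: ratio 1.00. Three sites: about 1% wider. Two sites: the ratio reverses, to 0.96 at r = 0.3 and 0.89 at r = 0.5, because very low degrees of freedom dominate.
- One-sided error at the threshold, 5 to 10 sites, no true site variance: 1.0–1.6% as written and 1.6–2.1% corrected, against a nominal 2.5%.

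**Power for the distance test** (true mean -0.057, 7 sites, r = 0.5, no true site variance):

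| assumed SD | 0.057/SD | as written | corrected | loss |
|---|---|---|---|---|
| 0.10 | 0.57 | 98.7% | 99.2% | 0.5 points |
| 0.12 | 0.475 | 93.7% | 95.3% | 1.6 points |
| 0.15 | 0.38 | 77.9% | 82.3% | 4.4 points |

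At near the margin is 0.17 − 0.091 = 0.079, and the loss over the same SDs is about 1 point or less.

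**The case against.** The strongest reply is that size and direction depend on inputs the documents do not contain, and that positive correlation cannot be taken for granted. These are multifocal lenses, and fitting can trade distance against near: the control fitting guide (Appendix H, Fitting Procedures, Step 4A) tries extra plus for near while checking that distance remains acceptable. Inclusion criterion 10 also narrows the range of corrected distance acuity. Only the average pairwise correlation drives the effect. With 0.3, 0 and 0.5 for the 4 m–64 cm, 4 m–40 cm and 64–40 cm pairs, the intervals are 3–4% wider with 5 to 10 sites; with 0.2, -0.2 and 0.4, about 2%. On that view r = 0.5 is a high scenario. Age and ADD power may also enter as covariates and absorb some shared variance, and section 14.1 calls the methods text a general description.

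Most of this stands and limits the size. It does not remove the gap, because no other section supplies a subject-level link. If a covariance over all six readings was intended, the present wording does not say so.

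A reader might also infer that standard errors will be 10–15% too large. Those closed-form figures precede truncation at zero and compare with the true SE. Against the model that would replace it, the difference is smaller.

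**Conclusion.** The covariance in section 14.6 is incompletely specified for a joint three-distance model. Given positive average correlation between distances and about five or more sites, the decisive intervals are on average about 2–8% too wide for r of 0.3–0.5, and the reported site variance is inflated. Both conditions are assumptions.

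Four stronger readings are tempting, and the documents do not support them:

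- **The intervals are too wide whatever the data.** There is no effect at r = 0, and with two sites the average width effect reverses.
- **A false success becomes more likely.** The error is conservative, so the cost is power.
- **The lens comparison is compromised.** Test-minus-Control differences at each distance are within subject, so site cancels. The CLUE model already groups errors by subject.
- **The trial's conclusions would change.** At the earlier study's means they probably would not, unless the acuity SD is near the top of the assumed range.

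It is a modest loss of precision in three required tests. It is worth correcting because the correction is cheap.

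**What to change.** In section 14.6, make the subject the independent unit. The preferred wording defines the residual covariance over all six readings of a subject: unstructured across the three distances, crossed with compound symmetry or unstructured across the two periods. A simpler fallback is to add a random subject intercept within site to the planned model. That forces one common, non-negative covariance on every pair of distances and would suit a distance–near trade-off less well.

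Leave the fixed effects, the Kenward-Roger method, the thresholds and the decision rules as they are. The cost is one sentence of text and one to a few more covariance parameters, with no new data. Making the change before unmasking avoids having to report it later as a deviation under section 14.10.

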Superiority will be declared if the upper limit of the 95% confidence interval of the adjusted mean for the Test lens is below 0.17 logMAR. i.e. $P(\mu_{Test} < 0.17) \geq 0.975$.

Clinical Study Protocol

Johnson & Johnson Vision Care, Inc.

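### Section 14.6 tests distance acuity against both 0 and 0.17 logMAR and gives no decision rule for the intermediate hypothesis that Section 2.3 requires

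*Combined protocol and SAP*

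**What the plan says.** Section 2.3 states that "All primary and secondary hypotheses must be met in order to satisfy the objective of this study". It lists two primary hypotheses on CLUE vision and three secondary hypotheses on acuity with the Test lens:

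1. "the mean distance visual acuity score of the Test lens will be statistically lower than 0.00 on logMAR scale"
2. "the mean intermediate visual acuity score of the Test lens will be statistically lower than 0.17 on logMAR scale"
3. "the mean near visual acuity score of the Test lens will be statistically lower than 0.17 on logMAR scale"

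Section 2.2 defines intermediate as 64 cm and near as 40 cm.

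Section 14.6 gives a null, an alternative and a decision rule for each of three secondary hypotheses:

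1. "binocular distance HLHC visual performance to test for superiority of the Test lens relative to the pre-defined threshold of 0 logMAR"
2. "binocular near HLHC visual performance to test for superiority of the Test lens relative to the pre-defined threshold of 0.17 logMAR"
3. "binocular distance HLHC visual performance to test for superiority of the Test lens relative to the pre-defined threshold of 0.17 logMAR"

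For the third, success is declared if "the upper limit of the 95% confidence interval of the adjusted mean for the Test lens is below 0.17 logMAR".

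The 64 cm measurement appears in Section 14.6 in two other places. It is a level of the distance factor in the mixed model, and it is one of the three distances at which a Test-minus-Control confidence interval is planned.

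**The concern.** The third rule in Section 14.6 names the wrong viewing distance. As printed, it asks a weaker question about a mean that the first rule has already tested, and the intermediate claim has no decision rule anywhere in Section 14. Sections 2.3 and 14.6 therefore define different success criteria. An analyst who programs Section 14.6 as it stands would report that every formal test passed without having compared intermediate acuity with its limit. Intermediate vision is a core property of a multifocal lens. If the conflict is noticed only after the data are seen, someone must choose a success criterion with the results in view.

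**Working it through.** **Comparison of the two sections (Test-lens mean, logMAR)**

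| Viewing distance | Section 2.3 | Section 14.6 |
|---|---|---|
| 4 m (distance) | hypothesis 1: below 0.00 | hypothesis 1: below 0; hypothesis 3: below 0.17 |
| 64 cm (intermediate) | hypothesis 2: below 0.17 | none |
| 40 cm (near) | hypothesis 3: below 0.17 | hypothesis 2: below 0.17 |

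In hypothesis 3, the word distance cannot be a general term for viewing distance. Hypothesis 1 uses the same phrase for the test against 0, and hypothesis 2 has near in the same position.

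**Redundancy.** Let U be the upper limit of the 95% interval for the adjusted Test mean at 4 m. Hypothesis 1 passes if U < 0 and hypothesis 3 passes if U < 0.17. Since 0 < 0.17, U < 0 implies U < 0.17.

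**Count.** Section 2.3 requires 2 + 3 = 5 criteria. Sections 14.5 and 14.6 list five tests: CLUE above 40, CLUE non-inferiority, distance below 0, near below 0.17, and distance below 0.17. The last is implied by the third, which leaves 5 − 1 = 4 distinct criteria.

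**Do the other 64 cm analyses fill the gap?** The planned 64 cm interval compares Test with Control and carries no threshold. It does not address whether the Test mean is below 0.17.

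**Illustration of size.** The documents give no power figure for the acuity hypotheses, so there is none to reproduce. Inputs:

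- n = 70 completers (Section 4.1).
- True Test means of −0.057 at distance and 0.091 at near, from the earlier study in Section 1.5. That section gives no intermediate value.
- SD of 0.08, 0.10 or 0.15 logMAR, assumed because the documents give none.
- Between-distance correlation of 0 or 0.5, assumed.
- Two-sided 95% t intervals, that is, one-sided 0.025 per criterion, in place of the full mixed model.

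Hand check at SD 0.15:

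- SE = 0.15/√70 = 0.0179, and the t quantile on 69 df is 1.995.
- Distance: 0.057/0.0179 − 1.995 ≈ 1.18, so the pass probability is about 0.88.
- Near: (0.17 − 0.091)/0.0179 − 1.995 ≈ 2.41, so it is about 0.99.
- Product, taking the two as independent: about 0.87.

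Simulation with 20,000 runs per setting gives the chance of passing all three secondary rules, shown as written → with hypothesis 3 on 64 cm. Ranges cover the two correlations.

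| True 64 cm mean | SD 0.08 | SD 0.10 | SD 0.15 |
|---|---|---|---|
| 0.10 | >0.99 → >0.99 | >0.99 → >0.99 | 0.87–0.88 → 0.84–0.86 |
| 0.12 | >0.99 → >0.99 | >0.99 → 0.98 | 0.87–0.88 → 0.68–0.73 |
| 0.17 | >0.99 → 0.024–0.025 | >0.99 → 0.024–0.025 | 0.87–0.88 → 0.020–0.025 |
| 0.20 | >0.99 → <0.001 | >0.99 → <0.001 | 0.87–0.88 → <0.001 |

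The as-written figures do not depend on the 64 cm mean. Removing hypothesis 3 altogether left the pass rate unchanged in every setting, as the logic requires.

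**The case against.** The strongest reply is that the success rule sits in Section 2.3, not Section 14.6, and Section 2.3 names the intermediate hypothesis. A lens with an intermediate mean of 0.25 would pass the printed tests but would not meet Section 2.3, so the documents contradict each other and do not adopt a weaker rule. Nothing ranks one section above the other. The slip also looks like a single wrong word: 0.17 is the intermediate limit in Section 2.3, the symbols in hypothesis 3 carry no distance label, and a deliberate second distance test would be pointless. A careful reader could recover the intent. It is a secondary hypothesis in a Phase 2b study, the primary tests are untouched, and the 64 cm data are measured and modelled.

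Much of this stands. It is a conflict between sections and very probably a copying error. The redundant test does not inflate the type I error, because all criteria must be met together. The 0.25 value and the simulated probabilities are illustrations, not forecasts.

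It does not remove the problem. Section 2.3 states the hypothesis but supplies no test, and Section 14.10 commits the analysis to the methods as specified, with any change justified in the report. That the intent can be inferred makes the repair easy; it does not put the rule in the plan.

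**Conclusion.** The point holds. Section 14 specifies no test of the intermediate hypothesis, and its Secondary hypothesis 3 is wrong as written. One of the five criteria required for success has no decision rule, and the five printed tests reduce to four. This follows from the text and from simple logic, with no assumption about the data.

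The size depends on the assumptions shown. At a true intermediate mean of exactly 0.17, the secondary rules pass about 0.87 to over 0.99 of the time as written, against about 0.020 to 0.025 with the intended test. For a lens comfortably inside the limit (true mean 0.10), adding the test costs at most about 2.4 percentage points (0.868 to 0.844 at SD 0.15, correlation 0). Nearer the limit and with a large SD it costs more: at a mean of 0.12 and SD 0.15, the pass rate falls from about 0.87–0.88 to 0.68–0.73. That is the ordinary cost of a criterion Section 2.3 already requires. It should be corrected before database lock.

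**What to change.** In Section 14.6, Secondary hypothesis 3, replace distance with intermediate (64 cm). Keep H0: μ_Test ≥ 0.17, HA: μ_Test < 0.17, and the requirement that the upper 95% limit of the adjusted Test mean at 64 cm is below 0.17. Then reorder hypotheses 2 and 3 so that intermediate is 2 and near is 3, as in Section 2.3.

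The cost is a small wording change. The 64 cm acuity is already measured at Visits 3 and 6 (Section 7.2, steps 3.8 and 6.8), and the model already yields the adjusted mean at that distance. Alpha, sample size and visit procedures do not change. Because the rule is part of the protocol, the change is a protocol revision and goes to the IEC/IRB where appropriate under Section 18.3.
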